8.3 Taper/Conversion Period (3 to 4 weeks \pm 1 week)

8.3.1 Telephone call (after 1 or 2 weeks in tapering/converting, as needed)

Subject will be interviewed to check his/her health condition including seizure experience, concomitant medications and procedures, and AEs.

8.3.2 Visit 8 (Week 19/20 \pm 1 week, end of Taper/Conversion)

The following procedures will be performed:

- Obtain C-SSRS data since the last visit
- Obtain CIWA-B data only for subjects tapering
- Measure vital signs (pulse rate, systolic BP, diastolic BP, and respiratory rate), in supine position after 5 minutes of rest
- Measure body weight
- Perform full physical examination (refer to [Section 11.3.4](#) for details)
- Perform full neurological examination (refer to [Section 11.3.5](#) for details)
- Perform Psychiatric and Mental Status assessment
- Obtain 12-lead ECG
- Collect blood and urine samples for clinical laboratory analyses
- Perform urine pregnancy test (female subjects of childbearing potential only)
- Seizure evaluation (count and type) from subject's daily record card
- Record concomitant medication (AEDs and non-AEDs) and procedures

- Record AEs
- Record health-related outcomes and HRU (refer to [Section 9.5](#) for details), with the exception of socio-professional status
- Check IMP accountability
- Study termination (only for subjects enrolling in OLE study, EP0093)

8.4 Safety Follow-Up (Visit 9 [Week 23 or earlier for EDV, approximately 30 days after last IMP intake])

The following procedures will be performed:

- Obtain C-SSRS data since the last visit
- Obtain HADS data
- Obtain SSG data
- Obtain QOLIE-31-P data
- Obtain CIWA-B data
- Measure vital signs (pulse rate, systolic BP, diastolic BP, and respiratory rate), in supine position after 5 minutes of rest
- Measure body weight
- Perform brief physical examination (refer to [Section 11.3.4](#) for details)
- Perform brief neurological examination (refer to [Section 11.3.5](#) for details)
- Perform Psychiatric and Mental Status assessment
- Obtain 12-lead ECG
- Obtain echocardiogram for subjects discontinuing the study (except if performed at Visit 6)
- Collect blood and urine samples for clinical laboratory analyses
- Perform urine pregnancy test (female subjects of childbearing potential only)
- Seizure evaluation (count and type) from subject's daily record card
- Record concomitant medication (AEDs and non-AEDs) and procedures
- Record AEs
- Record health-related outcomes and HRU (refer to [Section 9.5](#) for details), with the exception of socio-professional status
- End of diary recording
- Study termination, only for subjects who do not enter EP0093

An additional follow-up echocardiogram will be performed at 6 months (± 1 month) after the last IMP intake only for discontinued subjects exposed to IMP for more than 3 weeks and subjects not entering the OLE.

8.5 **Unscheduled Visit/Telephone call**

At any time, the subject may have an unscheduled study visit/telephone call if the Investigator and/or the subject deem it necessary. An unscheduled visit may be conducted due to safety or efficacy reasons and appropriate assessments will be conducted in relation to the reason for the visit. All information, including reason for visit/telephone call, any information on AEs, etc, should be collected in the source documents and recorded in the appropriate section of the eCRF.

8.6 **Open-label extension study (EP0093)**

Subjects from this study, have the option of taking PSL during an OLE study, EP0093. The decision to enter the OLE study must be made by the subject in consultation with the Investigator and/or the subject's caregiver. This decision must take into account the potential risks of long-term exposure to PSL and the potential benefit and risks of other treatment options available.

9 **ASSESSMENT OF EFFICACY**

The efficacy variables are described in detail in [Section 4.1](#).

9.1 **Seizure frequency**

At the Screening Visit (Visit 1), seizure count will be based on Investigator assessment of subjects' reports during the 8 weeks prior to the Screening Visit (Visit 1). The subject should report on average a minimum of 4 spontaneous and observable focal-onset seizures per 28 days with at least 1 seizure during each 4-week interval of the 8-week retrospective baseline. During the 4-week Baseline Period, the subject should experience a minimum of 4 spontaneous and observable focal-onset (based on Investigator assessment of subject report). During the study, subjects will keep diaries to record daily seizure activity from the Screening Visit (Visit 1) until the end of study participation. Subjects should be reminded to bring their diaries with them to each clinic visit.

The written information will be discussed with the subjects at each visit in order to ensure completeness and accuracy. As a result of the discussion, the Investigator will assess and confirm the seizures according to the ILAE codes and record the seizure types and frequency in the eCRF/diary; he/she will also confirm the presence of AEs if applicable.

Subjects should record all types of seizures that occur in their diary and be educated to complete their diary entries after each seizure or at least once a day (eg, when taking evening tablets). A caregiver can assist in completing the diary if necessary. If the subject does not complete diary entry as per instruction, this may result in subject discontinuation from the study at any time by the Investigator or the Sponsor ([Section 6.3](#)).

The following seizure information will be recorded in the diary:

- Seizure type
- Seizure frequency

9.2 Seizure Severity Global Item

The SSG consists of 1 or 2 items from the Seizure Severity Questionnaire and asks the subjects to evaluate the severity of their seizures for the last 4 weeks and/or since the Baseline (in EP0091). The subjects should describe all types of seizures when answering the questions.

The SSG will be completed according to the tabular schedule of study procedures, [Table 5-1](#). At the very beginning of the visit, the SSG will be provided to all subjects. It is preferred that the subject complete the questionnaire on his/her own; however, assistance may be provided by either the study staff or caregiver if needed. Once completed, the subject will return the completed questionnaire to the Investigator or designee, who will verify that all questions have been answered. Further details about the SSG will be covered in the Study Manual.

9.3 Quality of Life Inventory in Epilepsy-31-P

The QOLIE-31-P assesses subject functioning and health-related quality of life.

The QOLIE-31-P (Cramer et al, 2003) is an adaptation of the original QOLIE-31 instrument (Cramer et al, 1998) that includes 31 items grouped into 7 multi item subscales (Seizure Worry [5 items], Overall Quality of Life [2 items], Emotional Well-being [5 items], Energy/Fatigue [4 items], Cognitive Functioning [6 items], Medication Effects [3 items], and Daily Activities/Social Functioning [5 items]) and 1 health status item.

In addition to the 31 items of the QOLIE-31, the QOLIE-31-P contains 7 items assessing the degree of “distress” associated with the topic of each subscale (ie, distress items) and 1 item asking about the relative importance of each subscale topic (ie, prioritization item).

The QOLIE-31-P will be completed according to the tabular schedule of study procedures in [Table 5-1](#). At the very beginning of the visit, the QOLIE-31-P will be provided to all subjects. It is preferred that the subject will be asked to complete the questionnaire on his/her own; however, assistance may be provided by the study staff or caregiver if needed. Once completed, the subject will return the completed questionnaire to the Investigator or designee, who will verify that all questions have been answered. Further details about the QOLIE-31-P will be covered in the Study Manual.

9.4 Hospital Anxiety and Depression Scale

The HADS was chosen for its well-established psychometric properties both in general population and more recently in patients with epilepsy (Lin and Pakpour, 2017; Wiglusz et al, 2016; de Oliveira et al, 2014). The HADS scores for anxiety and for depression range from 0-21 with higher scores indicating worse state. A score below 8 is considered to be normal (Zigmond and Snaith, 1983). It is preferred that the subject complete the questionnaire on his/her own; however, assistance may be provided by either the study staff or caregiver if needed.

9.5 Health-related outcomes and healthcare resource utilization

Health-related outcomes and HRU will be collected in the eCRF and/or diary during the study according to the tabular schedule of study procedures, [Table 5-1](#).

These assessments will include:

- Socio-professional status
- Healthcare provider consultations not foreseen by protocol including the type of provider (general practitioner, specialist physician, nurse), the site of care (office-private, office-hospital, home, emergency room) and the reason leading to the consultation
- Concurrent medical procedures
- Concomitant medications
- Hospitalizations including the reason leading to the hospitalization, the admission ward transfers and length of stay
- Caregiver support needs
- Number of school or working days lost due to the medical condition of the subjects

9.6 Entry and exit personal outcomes interview

Participation in this additional portion of the study is optional and does not preclude participation in the main study. Please refer to [Section 13.4.3](#) for details on analysis of the corresponding data.

Subjects will be invited to participate in a qualitative interview that may last approximately 30 to 45 minutes (before treatment starts [Visit 1 or Visit 2]), and in another 30-minute qualitative interview at the end of the study (Visit 6 or Visit 7). For subjects who choose to participate, the interviews will be conducted by a study nurse/study personnel using a semi-structured interview guide and will be audio-recorded.

The aim of the entry interview is to gather insight into how epilepsy impacts the subject's life (beyond seizure count) across various domains (social, relationship, independence, work, psychological, etc), what is most restrictive for the subject, and to understand what would constitute a meaningful change when trying a new therapy and the trade-off across various domains.

The aim of the exit interview is to evaluate if and which aspects (domains) of the subject's life is impacted by the treatment and the extent to which the treatment achieves what is considered a meaningful change by the subject. If a subject leaves the study prematurely, he/she will also be invited to participate in an exit interview at this/her final visit (Visit 7).

9.7 Caregiver survey

Participation in the caregiver survey is optional and does not preclude a subject's participation in the main study. The caregiver optional survey aims to gather their perspective on the impact of epilepsy on the subject's life and expectations of meaningful change. The caregiver survey will also assess the impact of caring for a subject with epilepsy on his/her own life across various domains (social, relationship, independence, work, etc). This survey will allow UCB to gather differences in perspective and expectations from the subject and his/her caregiver's point of view.

Refer to [Section 13.4.3](#) for details on analysis of the corresponding data.

10 ASSESSMENT OF PHARMACOKINETIC AND EXPLORATORY VARIABLES

Blood samples for PK and exploratory variables will be obtained at the scheduled time points presented in [Table 5-1](#) and details of the collection, storage, preparation, and shipping of samples will be presented in a Laboratory Manual.

10.1 Pharmacokinetic variables

The PK variables for parent PSL and metabolites are described in detail in [Section 4.3.1](#). Calculations of PK parameters will be made using population PK modeling. Additionally, plasma concentration data for concomitantly administered AEDs will be evaluated by comparing ratios of steady state levels vs Baseline levels. For details of PK analyses, refer to [Section 13.4.2](#).

Detailed information on the collection, storage, preparation, and shipping of samples will be presented in a Laboratory Manual.

10.1.1 PK sampling procedures

10.1.1.1 PSL assay

Subjects are requested to provide blood samples for measurement of PSL and metabolite levels whenever possible using the VAMS technology on the MITRA microsampling device. Site personnel are requested to discuss the importance of PK samples to measure blood levels of PSL and inform the selection of the safety and efficacy of the doses examined in this study. Site personnel should educate subjects regarding the importance of accurately recording the time of the last IMP intake and their concomitant AEDs.

On Visits 3, 5, and 6, site personnel should obtain blood samples for random PSL levels at any time between IMP intakes and record accurately the time of last IMP intake and time of the sample.

On Visits 4 and 7, blood samples for measurement of sparse PK profiles should be collected as follows: immediately before IMP intake (maximum 15 minutes before intake) and then 3 times after (between 30 minutes and 3 hours after IMP intake) taken at least 30 minutes apart.

All samples may be taken either at home or at the site when possible or partly at home and partly at the site.

10.1.1.2 Concomitant AED and exploratory pharmacokinetic evaluation

Subjects are requested to provide blood samples for concomitant AED assay (to evaluate any DDI with PSL) at Visits 1, 2, 6, and 7.

On Visits 6 and 7, if the time point of sampling is not within 5 minutes of 1 of the scheduled PSL PK collections, then an additional MITRA sample will be taken alongside (± 5 minutes) the concomitant AED sample. This process will only be done at some pre-selected sites for a limited number of subjects.

Assay of PSL metabolites may be included in the concomitant AED assay screen.

10.2 Exploratory variables

Detailed information on the collection, storage, preparation, and shipping of samples for DNA, RNA, lipidomics, and proteomics analysis will be presented in a Laboratory Manual.

Results for the exploratory parameters obtained from DNA, RNA, lipidomics, and proteomics analysis, and serum biomarkers will be described in a separate report.

11 ASSESSMENT OF SAFETY

11.1 Adverse events

11.1.1 Definitions

11.1.1.1 Adverse events

An AE is any untoward medical occurrence in a patient or clinical investigation subject administered a pharmaceutical product that does not necessarily have a causal relationship with this treatment. An AE can therefore be any unfavorable and unintended sign (including an abnormal laboratory or echocardiogram finding), symptom, or disease temporally associated with the use of a medicinal (investigational) product, whether or not related to the medicinal (investigational) product.

In order to ensure complete safety data collection, all AEs occurring during the study (ie, after the signing of the ICF until the SFU Visit), including any pretreatment and posttreatment periods required by the protocol, must be reported in the eCRF even if no IMP was taken but specific study procedures were conducted. This includes all AEs not present prior to the initial visit and all AEs that recurred or worsened after the initial visit.

Signs or symptoms of the condition/disease for which the IMP is being studied (ie, seizures) should be recorded as AEs only if their nature changes considerably or their frequency or intensity increases in a clinically significant manner as compared with the clinical profile known to the Investigator from the subject's history or the Baseline Period.

11.1.1.2 Serious adverse events

Once it is determined that a subject experienced an AE, the seriousness of the AE must be determined. An SAE must meet 1 or more of the following criteria:

- Death
- Life-threatening
(Life-threatening does not include a reaction that might have caused death had it occurred in a more severe form.)
- Significant or persistent disability/incapacity
- Congenital anomaly/birth defect (including that occurring in a fetus)
- Important medical event that, based upon appropriate medical judgment, may jeopardize the subject and may require medical or surgical intervention to prevent 1 of the other outcomes listed in the definition of serious

(Important medical events may include, but are not limited to, potential Hy's Law [see [Section 11.1.1.2.2](#)], allergic bronchospasm requiring intensive treatment in an emergency

room or at home, blood dyscrasias that do not result in inpatient hospitalization, or the development of drug dependency or drug abuse)

- Initial inpatient hospitalization or prolongation of hospitalization

(A patient admitted to a hospital, even if he/she is released on the same day, meets the criteria for the initial inpatient hospitalization. An emergency room visit that results in admission to the hospital would also qualify for the initial inpatient hospitalization criteria. However, emergency room visits that do not result in admission to the hospital would not qualify for this criteria and, instead, should be evaluated for 1 of the other criteria in the definition of serious [eg, life-threatening adverse experience, important medical event].

Hospitalizations for reasons not associated with the occurrence of an AE [eg, preplanned surgery or elective surgery for a pre-existing condition that has not worsened or manifested in an unusual or uncharacteristic manner] do not qualify for reporting. For example, if a subject has a condition recorded on his/her medical history and later has a preplanned surgery for this condition, it is not appropriate to record the surgery or hospitalization as an SAE, since there is no AE upon which to assess the serious criteria. Please note that, if the pre-existing condition has worsened or manifested in an unusual or uncharacteristic manner, this would then qualify as an AE and, if necessary, the seriousness of the event would need to be determined.)

11.1.1.2.1 Anticipated serious adverse events

The following anticipated SAEs are anticipated to occur in the epilepsy population at some frequency that is independent of drug exposure.

This list does not change the Investigator's obligation to report all SAEs (including Anticipated SAEs) as detailed in [Section 11.1.2.3](#).

Table 11–1: Anticipated SAEs for the epilepsy population

MedDRA System Organ Class	MedDRA Preferred Term
Congenital and hereditary disorders	Teratogenicity
General disorders and administration site conditions	Sudden unexplained death in epilepsy
Injury, poisoning, and procedural complication	Fall ^a , fracture ^a , injury ^a
Nervous system disorders	Cluster seizures, convulsion, incontinence ^a memory impairment, status epilepticus
Pregnancy, puerperium, and perinatal disorders	Abortion spontaneous
Psychiatric disorders	Abnormal behavior, acute psychosis, anxiety, cognitive disorder, confusional state, psychotic behavior, sleep disorder and disturbances
Reproductive system and breast disorders	Impotence, menstrual disorder

MedDRA=Medical Dictionary for Regulatory Activities, Version 19.1; SAE=serious adverse event; SOC=System Organ Class

^a Event are anticipated when occurring in the context of seizure, but not classified in MedDRA primary SOC.

11.1.1.2.2 Adverse events of special interest

Potential Hy's Law, defined as $\geq 3 \times \text{ULN}$ ALT or AST with coexisting $\geq 2 \times \text{ULN}$ total bilirubin in the absence of $\geq 2 \times \text{ULN}$ ALP, with no alternative explanation for the biochemical abnormality, must ALWAYS be reported to UCB as an AE of special interest (ie, without waiting for any additional etiologic investigations to have been concluded). Follow-up information should then be reported if an alternative etiology is identified during investigation and monitoring of the subject.

11.1.2 Procedures for reporting and recording adverse events

The subject will be given the opportunity to report AEs spontaneously. A general prompt will also be given at each study visit to detect AEs. For example:

“Did you notice anything unusual about your health (since your last visit)?”

In addition, the Investigator should review any self-assessment procedures (eg, diary cards) employed in the study.

11.1.2.1 Description of adverse events

When recording an AE, the Investigator should use the overall diagnosis or syndrome using standard medical terminology, rather than recording individual symptoms or signs. The eCRF and source documents should be consistent. Any discrepancies between the subject's own words on his/her own records (eg, diary card) and the corresponding medical terminology should be clarified in the source documentation.

Details for completion of the Adverse Event eCRF (including judgment of relationship to IMP) are described in the eCRF Completion Guidelines.

11.1.2.2 Rule for repetition of an adverse event

An increase in the intensity of an AE should lead to the repetition of the AE being reported with:

- The outcome date of the first AE that is not related to the natural course of the disease being the same as the start date of the repeated AE, and the outcome of “worsening”
- The AE verbatim term being the same for the first and repeated AE, so that the repeated AE can be easily identified as the worsening of the first one

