## 10.2 Adverse events

Adverse events are recorded on the AE CRF as they occur, from the time informed consent is granted until study completion or study termination (end of the SFU period 30 days after the last IMP intake). All AEs will be coded using the latest available version of MedDRA.

A treatment-emergent adverse event (TEAE) is defined as any event not present prior to the initiation of the first dose of study treatment or any unresolved event already present before initiation of the first dose that worsens in intensity following exposure to the treatment. The number and percentage of subjects who experience TEAEs at any time during the study will be summarized by SOC and PT. The following tabular summaries will be presented for the SS:

- Incidence of pre-treatment AEs. Pre-treatment AEs are AEs with start dates prior to the date of first dose of IMP.
- Incidence of TEAEs during the Treatment Period – Overview. Of note, the corresponding table is required for data transparency reporting.
- Incidence of TEAEs by period (Treatment Period, Titration and Stabilization Period, Maintenance Period, Conversion Period, and Taper and SFU Period)
- Incidence of Serious TEAEs by period (Treatment Period, Titration and Stabilization Period, and Maintenance Period)
- Incidence of TEAEs leading to discontinuation by period (Treatment Period, Titration and Stabilization Period, and Maintenance Period)
- Incidence of TEAEs leading to dose reduction during the Stabilization Period

The following will be presented for TEAEs during the overall Treatment Period:

- Subject numbers for TEAEs
- Incidence of TEAEs occurring in at least 5% of subjects in any treatment group

- Incidence of TEAEs occurring in at least 2% of subjects in any PSL group and greater than placebo group
- Incidence of TEAEs by Relationship
- Incidence of TEAEs by Maximum Intensity
- Incidence of TEAEs of special interest
- Incidence of SAEs by Relationship. Of note, the corresponding table is required for data transparency reporting.
- Incidence of Fatal TEAEs by Relationship. Of note, the corresponding table is required for data transparency reporting.
- Incidence of Non-Serious TEAEs above the threshold of 5% of subjects in any treatment group. Of note, the corresponding table is required for data transparency reporting.

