- Summary of the duration in days per event for the following TEAEs: somnolence, dizziness, fatigue, irritability and headache. In this analysis, if an AE is ongoing, the duration will be calculated till the date of final contact.

Summaries will be presented based on standard Sponsor AE table formats and considering formats used for the PSL program.

Where dates are missing or partially missing, AEs will be assumed to be treatment-emergent, unless there is unmistakable evidence (through comparison of partial dates, see Section 4.2) to suggest that the AE started prior to the first dose of study treatment. Summary tables will contain counts of subjects, percentages of subjects in parentheses and the number of events where applicable. A subject who has multiple events in the same MedDRA category (SOC or PT) will be counted only once in the subject count for that category, however all events will be included in the event count for the category. In summaries including relationship to study treatment, the following relationships will be summarized: 'Not related', 'Related'. A subject may be counted more than once according to the relationship to study treatment. Events with missing relationship will be considered as 'Related' to the last given study product for summary purposes but recorded as missing in the listings. In summaries of the maximum intensity, the following intensity categories will be summarized: 'Mild', 'Moderate', 'Severe'. Subjects who experience the same event multiple times, with differing severities, will be included in the most severe category. Events with missing intensity will be considered as 'Severe' events for summary purposes but recorded as missing in the listings. The main reasons for treatment discontinuation will be listed by subject. The daily dose of study medication corresponding to the AE onset date will be included in the listing. Daily dose will be derived from 'Study Medication Administration' CRF.

Adverse event summaries will be ordered in terms of decreasing frequency for SOC, and PT within SOC, within the PSL total group column.

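### SAP 10.2 reports adverse event duration per event without rejoining the records that Protocol 11.1.2.2 splits at each worsening, so mean duration is understated

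*Protocol*

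**What the plan says.** Protocol 11.1.2.2 sets the recording rule: "An increase in the intensity of an AE should lead to the repetition of the AE being reported with" two features. First, the earlier entry gets an outcome of worsening and an outcome date "being the same as the start date of the repeated AE". Second, the two entries share a key: "The AE verbatim term being the same for the first and repeated AE, so that the repeated AE can be easily identified" as a worsening of the first.

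SAP 10.2 names its source: "Adverse events are recorded on the AE CRF as they occur". Among the outputs for the overall Treatment Period it lists: "Summary of the duration in days per event for the following TEAEs: somnolence, dizziness, fatigue, irritability and headache". The only handling rule for that table concerns unresolved events: "if an AE is ongoing, the duration will be calculated till the date of final contact". On counting, a subject with several events in one MedDRA category "will be counted only once in the subject count for that category", but "however all events will be included in the event count for the category". Where severities differ, the maximum-intensity table keeps the most severe.

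No current section of the SAP says what happens to an entry that ended only because its continuation was opened.

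**The concern.** The recording rule and the duration table use different units. Under the protocol, one uninterrupted episode that worsens becomes two contiguous AE entries, each with its own start and end. The SAP then averages days per event over whatever counts as an event. If that is the entry, a fully resolved episode of eight weeks that worsened halfway contributes two durations of about four weeks. This is separate from how ongoing events are closed, because it also shortens events that have ended.

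At stake is what the table tells a reader about how long these events last. All five terms are among the most frequent TEAEs listed for the earlier Phase 2 study in Protocol 2.3.1, so the table is likely to be read. If worsening is more common in some arms than others, the understatement is also unequal between them.

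**Working it through.** **Inputs.** The documents give no AE duration, no event count and no worsening rate, so there is no figure of the plan's own to reproduce. Two quantities are assumed:
- L, the true mean length of an episode;
- w, the share of episodes that worsen once, with both entries treatment-emergent. Range used: 5% to 50%.

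**Formula.** For N episodes, the total number of days is N × L whether or not entries are split, and the number of entries is N × (1+w). Hence:
- entries per episode = 1+w;
- mean days per entry = L/(1+w);
- relative understatement = 1 − 1/(1+w) = w/(1+w).

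The SAP gives no duration formula. If days are counted inclusively, the shared date is counted twice and the mean is (L+w)/(1+w), which changes little.

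**Results for L = 28 days (assumed).**

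| w | Entries per episode | Mean per entry, L/(1+w) | Inclusive, (L+w)/(1+w) | Understatement, w/(1+w) |
|---|---|---|---|---|
| 5% | 1.05 | 26.7 | 26.7 | 4.8% |
| 10% | 1.10 | 25.5 | 25.5 | 9.1% |
| 20% | 1.20 | 23.3 | 23.5 | 16.7% |
| 30% | 1.30 | 21.5 | 21.8 | 23.1% |
| 50% | 1.50 | 18.7 | 19.0 | 33.3% |

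The percentage in the last column does not depend on L. A second worsening adds a further entry: if 30% of episodes worsen twice, the mean is 28/1.6 = 17.5 days.

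**Two arms with the same true mean of 28 days.** With w = 5% in one and 30% in the other, the table would show 26.7 and 21.5 days (ratio 1.05/1.30 = 0.81). The number of events would be 1.30/1.05 = 1.24 times as large in the second arm for the same number of episodes. Rejoining the entries restores 28 days and a ratio of 1 in both.

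**If worsening episodes are longer.** Let them last r times as long as the others, whose mean is M. The true mean is M(1−w+rw), and the mean per entry is M(1−w+rw)/(1+w). At r = 2 the latter equals M for every w. With M = 22.5 days, arms at w = 5% and 30% truly average about 23.6 and 29.3 days, yet both show 22.5. At r = 3 they show 22.5 × 1.10/1.05 = 23.6 and 22.5 × 1.60/1.30 = 27.7 days, so the arm with more worsening still shows the longer mean.

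**Median.** In simulation at w = 30% with equal lengths, the mean fell from 22.5 to 17.3 days, and the median from 16 to 11 (exponential lengths) or from 20 to 15 (gamma lengths). A fall in the median is not guaranteed: durations of 1, 1 and 10 days have mean 4 and median 1, and splitting the 10 into 5 and 5 gives mean 3 and median 3.

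**The case against.** **The SAP does not define the unit.** It says per event, not per CRF entry, and it defers to sponsor table formats that are not shown and might contain a merging rule. That is fair. But the protocol treats the repeat as an AE with its own dates, the SAP draws on the AE CRF, and the SAP gives explicit rules for repeated events in subject counts and in maximum intensity but none for duration. An analyst following the text would average entries. A rule that exists only in an unseen format should be stated in the plan.

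**Counting a worsening as a separate event is defensible.** The TEAE definition in SAP 10.2 includes an existing event that worsens after the first dose, and by-period and by-relationship tables need the separate entries. This stands, and it is why the merge should not extend to event counts.

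**Not every worsening triggers the rule.** Protocol 11.1.2.2 refers to an AE unrelated to the natural course of the disease. This stands as a limit on w.

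**The dose gradient is assumed.** A reader might infer from Table 7-1, where the 800mg/day arm is raised in steps while the 100mg/day and placebo arms have none, that events will look shorter at high dose than on placebo. The documents do not support that. They give no worsening rate by arm. Titration ends with the target dose on Day 22, and the dose is then held stable through Maintenance. Subjects who cannot tolerate treatment before Week 3 leave the study, and one fallback is allowed. The r = 3 case above also shows that the arm with more worsening can still display the longer mean.

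**Conclusion.** The point holds for the duration table. Applied as written, the two rules cut one continuous episode into shorter pieces, and mean duration is understated by w/(1+w): about 5% to 33% for w between 5% and 50%. The downward direction is certain for the mean whenever any episode is split, but not for the median. The size rests on an assumed w. A difference between arms arises if w differs by arm, which the documents do not quantify.

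A reader might also infer that the secondary safety objective is compromised. It is not. The primary safety variables in Protocol 4.2.1 are incidences of TEAEs, of TEAEs leading to withdrawal and of serious TEAEs. Subjects are counted once per category, and maximum intensity takes the worst entry, so splitting changes none of these. AE duration and event counts are not in the lists of safety variables in Protocol 4.2 or SAP 2.4. What is affected is one descriptive five-term table, plus event-count columns that must be read as counts of entries.

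**What to change.** Add to SAP 10.2, for the duration summary only:
- Chain entries of the same subject with the same verbatim term where the earlier one has outcome worsening and the next starts on its outcome date.
- Compute duration per episode from the start of the first treatment-emergent entry in the chain to the end of the last, with the existing final-contact rule applied if the last is ongoing.

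Starting at the first treatment-emergent entry matters: chaining back to the first entry of any kind would bring pre-dose days into the duration of a TEAE that began as a pre-existing complaint.

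Leave the by-period, relationship and intensity tables on separate entries, and footnote event counts to say that each recorded worsening counts as a separate entry.

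The cost is a sentence or two in the SAP, one footnote and a short derivation. The linking fields (verbatim term, outcome, dates) are already required by Protocol 11.1.2.2, so no new data are needed.
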